10.5.3 Patient Reported Outcome Analysis Population

The PRO analyses are based on the PRO full analysis set (FAS) population, defined as participants who have received treatment and have at least one PRO assessment available.

10.6 Statistical Methods

10.6.1 Statistical Methods for Efficacy Analyses

This section describes the statistical methods that address the primary and secondary objectives. Methods related to exploratory objectives will be described in the sSAP.

Efficacy results that will be deemed to be statistically significant after consideration of the Type I error control strategy are described in Section 10.8, Multiplicity. Nominal p-values

may be computed for other efficacy analyses, but should be interpreted with caution due to potential issues of multiplicity.

The 3 stratification factors used for randomization, including primary tumor site, tumor stage, and PD-L1 status defined by TPS 50% will be applied to all stratified analyses; in particular, stratified log-rank test, stratified Cox model, and stratified Miettinen and Nurminen method [Miettinen, O. and Nurminen, M. 1985]. For participants who were randomized prior to Amendment 04 without stratification factor for PD-L1 status at randomization, the TPS raw score will be used retrospectively to derive the stratification factor for PD-L1 status in the analyses. In the event that there are small strata, for the purpose of analysis, strata will be combined to ensure sufficient number of participants, responses or events in each stratum. Details regarding the pooling strategy will be pre-specified in the sSAP prior to the database lock for **CCI** [REDACTED], based on a blinded review of participants and event counts by stratum.

10.6.1.1 Event-Free Survival

The non-parametric Kaplan-Meier method will be used to estimate the EFS curve in each treatment group. The treatment difference in EFS will be assessed by the stratified log-rank test. A stratified Cox proportional hazard (PH) model with Efron's method of tie handling will be used to assess the magnitude of the treatment difference (ie, HR) between the treatment arms. The HR and its 95% CI from the stratified Cox model with Efron's method of tie handling and with a single treatment covariate will be reported. The stratification factors used for randomization (see Section 7.3) will be applied to both the stratified log-rank test and the stratified Cox model.

Since disease progression/recurrence is assessed periodically, disease progression/recurrence can occur any time in the time interval between the last assessment where the event was not documented and the assessment when the event is first documented. The true date of disease progression/recurrence will be approximated by the date of the first assessment at which the event is objectively documented. Death is always considered as an event. Participants who do not experience a disease progression/recurrence event will be censored at the last disease assessment. Sensitivity analyses will be performed for comparison of EFS based on investigator's assessment.

In order to evaluate the robustness of the EFS endpoint, 1 primary and 1 sensitivity analyses with a different set of censoring rules will be performed. The primary analysis follows the Intention-To-Treat principle. That is, PDs/ recurrences/deaths are counted as events regardless of missed study visits or initiation of new anticancer therapy. For the sensitivity analysis, if the events (disease progression, recurrence or death) are immediately after more than 1 missed disease assessment, the data are censored at the last disease assessment prior to missing visits. Also data after new anticancer therapy are censored at the last disease assessment prior to the initiation of new anticancer therapy. If a participant meets multiple criteria for censoring, the censoring criterion that occurs earliest will be applied. The censoring rules for primary and sensitivity analyses are summarized in [Table 13](#).

Table 13 Censoring Rules for Primary and Sensitivity Analyses of EFS

Situation	Primary Analysis	Sensitivity Analysis
Disease progression, recurrence, or death documented after ≤ 1 missed disease assessment and before new anticancer therapy, if any	EFS event at date of documented disease progression, recurrence, or death	EFS event at date of documented disease progression, recurrence, or death
Disease progression, recurrent or death documented immediately after ≥ 2 consecutive missed disease assessments or after new anticancer therapy, if any	EFS event at date of documented disease progression, recurrence, or death	Censored at last disease assessment prior to the earlier date of ≥ 2 consecutive missed visits and new anticancer therapy, if any
No disease progression, no recurrence and no death; and new anticancer therapy is not initiated	Censored at last disease assessment	Censored at last disease assessment
No disease progression, no recurrence and no death; new anticancer therapy is initiated	Censored at last disease assessment	Censored at last disease assessment before new anticancer therapy
Abbreviations: EFS = event-free survival		

10.6.1.2 Major Pathological Response

mPR rate is defined as the proportion of participants with an mPR. The stratified Miettinen and Nurminen's method with strata weighting by sample size will be used for the comparison of mPR rates between the pembrolizumab arm and SoC arm. The stratification factors used for randomization (see Section 7.3) will be applied to the stratified Miettinen and Nurminen's method.

Participants who are discontinued from the study treatment and continue with other neoadjuvant treatment not specified by the study prior to definitive surgery will be classified as not having an mPR (non-responders) in the efficacy analyses, regardless of the results obtained from the surgery. Participants who are discontinued from study treatment due to the reasons that preclude surgery are considered non-responders.

10.6.1.3 Overall Survival

The non-parametric Kaplan-Meier method will be used to estimate the survival curves. The treatment difference in survival will be assessed by the stratified log-rank test. A stratified Cox PH model with Efron's method of tie handling will be used to assess the magnitude of the treatment difference (ie, the HR). The HR and its 95% CI from the stratified Cox PH model with Efron's methods of tie handling and with a single treatment covariate will be reported. The stratification factors used for randomization (see Section 7.3) will be applied to both the stratified log-rank test and the stratified Cox model.

10.6.1.4 Pathological Complete Response

pCR rate is defined as the proportion of participants with a pCR. The same method used to analyze mPR rate will be used to analyze pCR rate.

10.6.1.5 Summary of Efficacy Analysis Methods

[Table 14](#) summarizes the primary analysis approach for primary and secondary efficacy endpoints.

Table 14 Analysis Strategy for Primary and Secondary Efficacy Endpoints

Endpoint/Variable (Description, Time Point)	Statistical Method [†]	Analysis Population	Missing Data Approach
Primary:			
EFS	Test: stratified Log-rank test Estimation: stratified Cox model with Efron's tie handling method	ITT • Participants whose tumors express PD-L1 CPS \geq 10 • Participants whose tumors express PD-L1 CPS \geq 1 • All participants	• Primary censoring rule • Sensitivity analysis 1 (More details are in Table 13)
Secondary:			
mPR	Stratified M&N method	ITT • Participants whose tumors express PD-L1 CPS \geq 10 • Participants whose tumors express PD-L1 CPS \geq 1 • All participants	Participants with relevant data missing are considered non-responders
OS	Test: stratified Log-rank test Estimation: stratified Cox model with Efron's tie handling method	ITT • Participants whose tumors express PD-L1 CPS \geq 10 • Participants whose tumors express PD-L1 CPS \geq 1 • All participants	Censored at last date participant was known to be alive
pCR	Stratified M&N method	ITT • Participants whose tumors express PD-L1 CPS \geq 10 • Participants whose tumors express PD-L1 CPS \geq 1 • All participants	Participants with relevant data missing are considered non-responders

[†] Statistical models are described in further detail in the text. For stratified analyses, the stratification factors used for randomization (see Section 7.3.1 – Stratification) will be applied to the analysis model.
 
Abbreviations: CPS = combined positive score; EFS = Event-free survival; ITT = Intention-To-Treat; M&N = Miettinen and Nurminen; mPR = major pathological response; OS = overall survival; pCR = pathological complete response; PD-L1 = programmed cell death ligand 1.
			

10.6.2 Statistical Methods for Safety Analyses

Safety and tolerability will be assessed by clinical review of all relevant parameters including AEs, laboratory tests, and vital signs.

The overall safety evaluation will include a summary of the number and percentage of participants with at least one AE, drug-related, SAE, serious drug-related AE, Grade 3-5 AE, drug-related Grade 3-5 AE, discontinuation from study intervention due to an AE, and an AE resulting in death.

The number and percentage of participants with specific AEs will also be provided. Point estimate and 95% CIs for the difference between treatment groups in the percentage of participants with specific AEs will be provided for AEs that occur in at least 10% of participants in any treatment group. The threshold of at least 10% of participants was chosen because the population enrolled in this study is in critical condition and usually experiences various AEs of similar types regardless of treatment; events reported less frequently than 10% of participants would obscure the assessment of the overall safety profile and add little to the interpretation of potentially meaningful treatment differences. In addition, difference in the percentage of participants with specific Grade 3-5 AEs ($\geq 5\%$ of participants in any treatment group) and SAEs ($\geq 5\%$ of participants in any treatment group) will also be summarized by point estimate and 95% CI. Rainfall plots with point estimates and 95% CIs will be displayed for specific AEs, specific Grade 3-5 AEs and specific SAEs that meet the corresponding predefined threshold rules.

CIs for between treatment group differences will be provided using the M&N method [Miettinen, O. and Nurminen, M. 1985]. Because many 95% CIs may be provided without adjustment for multiplicity, the CIs should be regarded as helpful descriptive measures for the review of the safety profile and not as a formal method for assessing the statistical significance of the between-group differences.

The number and percentage of participants with laboratory toxicity grade increased from baseline will be summarized by the post-baseline maximum toxicity grade per CTCAE V4.0 for each gradable laboratory test. For continuous safety measures, such as change from baseline in laboratory and vital signs, summary statistics for baseline, on-treatment, and change from baseline values will be provided.

Assessment of Safety Topics of Special Interest

AEs that are immune-mediated or potentially immune-mediated are considered safety topics of special interest (AEOSI) in this study. These events have been characterized consistently throughout the pembrolizumab clinical development program. Point estimates and 95% CIs for between-group difference is not expected to add value to the safety evaluation, and hence only number and percentage of participants with such pembrolizumab AEOSI will be provided, as well as the number and percentage of participants with corticosteroids administration to treat an AEOSI. Summary statistics will be provided for the analysis of time from first dose to the onset of an AEOSI.

Table 15 Analysis Strategy for Safety Parameters

Analysis Part	Safety Endpoint	95% CI for Treatment Comparison	Descriptive Statistics
Overall Safety Assessment	Specific Grade 3-5 AE (incidence $\geq 5\%$ of participants in one of the treatment groups)	X	X
	Specific serious AE (incidence $\geq 5\%$ of participants in one of the treatment groups)	X	X
	Specific AEs, SOCs (incidence $\geq 10\%$ of participants in one of the treatment groups)	X	X
	Any AE		X
	Any Grade 3-5 AE		X
	Any Serious AE		X
	Any Drug-Related AE		X
	Any Serious and Drug-Related AE		X
	Any Grade 3-5 and Drug-Related AE		X
	Discontinuation due to AE		X
Assessment of safety topics of special interest	Death		X
	Specific AEs, SOCs (incidence $> 0\%$ of participants in all of the treatment groups)		X
Assessment of safety topics of special interest	Change from Baseline Results (lab toxicity shift)		X
	Pembrolizumab AEOSI		X
Abbreviations: AE = adverse event; AEOSI = adverse event of special interest; CI = confidence interval; SOC = system organ class.			

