- c The timeframe for surgery (after the presurgery visit) is 6 weeks (± 10 days) after randomization. Participants in Arm A are allowed to go to surgery outside of this timeframe if delays are due to an AE. Participants with delays other than for an AE may be considered with sponsor consultation.

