Note: 2 doses of study medication (pembrolizumab) are administered prior to surgery, at 3-week intervals from the date of the first dose. A subsequent 15 doses are administered post-surgery, calculated in 3-week intervals from the date of the first dose post-surgery.

- Administrative reasons.

Refer to Appendix 8 for additional Germany-specific guidance.

For participants who are discontinued from study treatment but continue to be monitored in the trial, all visits and procedures, as outlined in the SoA, should be completed.

Discontinuation from study treatment is "permanent." Once a participant is discontinued, he/she shall not be allowed to restart study treatment.

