9.3 Adverse Events, Serious Adverse Events and Other Reportable Safety Events

The definitions of an adverse event (AE) or serious adverse event (SAE), as well as the method of recording, evaluating, and assessing causality of AE and SAE and the procedures for completing and transmitting AE, SAE and other reportable safety event reports can be found in Appendix 4.

AE, SAEs, and other reportable safety events will be reported by the participant (or, when appropriate, by a caregiver, surrogate, or the participant's legally authorized representative).

The investigator, who is a qualified physician, and any designees are responsible for detecting, assessing, documenting, and reporting events that meet the definition of an AE or SAE as well as other reportable safety events. Investigators need to document if an SAE was associated with a medication error, misuse, or abuse. Investigators remain responsible for following up AE, SAEs and other reportable safety events for outcome according to Section 9.3.3.

Adverse events will not be collected for participants during the pre-screening period (for determination of archival tissue status) as long as that participant has not undergone any protocol-specified procedure or intervention. If the participant requires a blood draw, fresh tumor biopsy etc., the participant is first required to provide consent to the main study and AEs will be captured according to guidelines for standard AE reporting.

9.3.1 Time Period and Frequency for Collecting AE, SAE and Other Reportable Safety Event Information

AEs, SAEs, and other reportable safety events that occur after the participant provides documented informed consent, but before treatment allocation/randomization, must be reported by the investigator if the event causes the participant to be excluded from the trial, or is the result of a protocol-specified intervention, including, but not limited to washout or discontinuation of usual therapy, diet, or a procedure.

- All AEs from the time of treatment allocation/randomization through 30 days following cessation of study treatment must be reported by the investigator.
- All adverse events considered to be post-surgical complications by the investigator from time of protocol-specified surgery through 30 days following surgery, must be reported by the investigator.

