- All AEs meeting serious criteria, from the time of treatment allocation/randomization through 90 days following cessation of study treatment, or 30 days following cessation of study treatment if the participant initiates new anticancer therapy, whichever is earlier must be reported by the investigator.
- All SAEs that are considered to be post-surgical complications by the investigator, from the time of protocol-specified surgery through 90 days following surgery or 30 days following protocol-specified surgery if the subject initiates new anticancer therapy, whichever is earlier, must be reported by the investigator.
- All pregnancies and exposure during breastfeeding, from the time of treatment allocation/randomization through the time required to eliminate systemic exposure after cessation of study treatment as described in Sections 6.1 and 9.5.9.2, or 30 days after cessation of study treatment if the participant initiates new anticancer therapy must be reported by the investigator.
- Additionally, any SAE brought to the attention of an investigator at any time outside of the time period specified above must be reported immediately to the Sponsor if the event is considered to be drug-related. Subjects in post-treatment follow-up will be actively followed for treatment-related late SAEs for up to 5 years.

Investigators are not obligated to actively seek AE or SAE or other reportable safety events in former study participants. However, if the investigator learns of any SAE, including a death, at any time after a participant has been discharged from the study, and he/she considers the event to be reasonably related to the study treatment or study participation, the investigator must promptly notify the sponsor.

All initial and follow-up AEs, SAEs and other reportable safety events will be recorded and reported to the sponsor or designee within the timeframes as indicated in [Table 12](#).

Table 12 Reporting Time Periods and Timeframes for Adverse Events and Other Reportable Safety Events

Type of Event	Reporting Time Period: Consent to Randomization/Allocation	Reporting Time Period: Randomization/Allocation through Protocol-Specified Follow-up Period	Reporting Time Period: After the Protocol Specified Follow-up Period	Timeframe to Report Event and Follow-up Information to SPONSOR:

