9.10.2.1 Neoadjuvant Treatment (Treatment 1)

Only participants in Treatment Arm A/pembrolizumab will receive neoadjuvant pembrolizumab; participants in Treatment Arm A/pembrolizumab should proceed to surgery directly following the presurgery visit (within 6 weeks [\pm 10 days]) after randomization). Participants in Arm A are allowed to go to surgery outside this timeframe if delays are due to an AE. Participants with delays other than for an AE may be considered with sponsor consultation. Participants in the Treatment Arm B/SoC will proceed directly to surgery following within 4 weeks after randomization.

Visit timing requirements during the treatment period for Arm A are as follows:

- Assessments/procedures should be performed on Day 1 for each cycle.
- Pembrolizumab treatment cycles are 3 weeks (21 days).
- The window for each visit is \pm 3 days, unless otherwise noted. Cycle 1 treatment should begin within 3 days of randomization or as close as possible to that date on which the participant is allocated or assigned.

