9.10.3.3 Follow-up Visits

Participants who complete study treatment or discontinue study treatment for a reason other than an event/disease progression/recurrence will move into the Post-Treatment Follow-up Phase and should be assessed in office every 3 months (91 ± 7 days) until the end of Year 3 (measured from the date randomization) to monitor disease status. In Years 4 and 5, participants should be assessed in office every 6 months (182 ± 14 days) to monitor disease status. After Year 5, participants will move into Survival Follow-up. Any additional tests/investigations or imaging assessments for progressive/recurrent disease or safety will be at the discretion of participant's treating physician per local SoC. Every effort should be made to collect information regarding disease status until an event/disease progression, death, withdrawal of consent or end of study. Information regarding post-study anticancer treatment will be collected if new treatment is initiated. Participants who have completed all efficacy assessments must enter Survival Follow-up. Participants who discontinue efficacy assessments early, and have not experienced an event/progression, will be requested for standard of care imaging assessments/biopsy to evaluate disease status.

For a participant who dies during the Follow-up period, date and cause of death should be recorded in the appropriate eCRF.

Participants in Post-Treatment Follow-up will be followed for treatment-related late toxicities for up to Year 5 and should be recorded.

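### Specific-AE percentages are compared between arms over about 58 weeks of collection in Arm A and 21 in Arm B (treatment completers), with no phase- or exposure-adjusted summary

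*Combined protocol and SAP*

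**What the plan says.** Section 10.6.2 and Table 15 plan between-arm differences with Miettinen and Nurminen (M&N) 95% CIs, and rainfall plots, for three groups of events: specific AEs (at least 10% in an arm), specific Grade 3-5 AEs (at least 5%) and specific SAEs (at least 5%). For the first group the text reads: "Point estimate and 95% CIs for the difference between treatment groups in the percentage of participants with specific AEs will be provided". The any-AE, any-Grade 3-5, any-SAE and AEOSI rows carry no between-arm CI and are not at issue.

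Section 9.3.1 sets the collection periods: "All AEs from the time of treatment allocation/randomization through 30 days following cessation of study treatment must be reported by the investigator" and "All AEs meeting serious criteria, from the time of treatment allocation/randomization through 90 days following cessation of study treatment". The SAE period shortens to 30 days if new anticancer therapy starts. Beyond these periods, both arms are followed for treatment-related late events only: "Subjects in post-treatment follow-up will be actively followed for treatment-related late SAEs for up to 5 years" (Section 9.3.1) and "Participants in Post-Treatment Follow-up will be followed for treatment-related late toxicities for up to Year 5 and should be recorded" (Section 9.10.3.3).

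Treatment length differs by design. In Arm A, Section 8.1 states: "A subsequent 15 doses are administered post-surgery, calculated in 3-week intervals from the date of the first dose post-surgery". In Arm B, study treatment ends with RT ± cisplatin (Section 2.3).

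**The concern.** A percentage of participants with an event grows with the time over which events are counted. Arm A is observed for AEs through the whole pembrolizumab-only phase, which has no counterpart in Arm B. For events not confined to surgery and radiotherapy, the planned difference mixes pembrolizumab toxicity with longer observation. Acute radiotherapy reactions (Section 9.1.10.1.2.3) and surgical complications occur mainly in a phase both arms share, so they are little affected. The events most exposed are background or intercurrent ones not judged treatment-related, because the follow-up to Year 5 does not pick those up.

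No planned summary puts the arms on a common time base. Time to onset is planned for AEOSI only, and extent of exposure (Section 10.12) counts cycles without linking them to AEs. The plan also does not say whether late-toxicity records up to Year 5 enter the percentages. At stake is the reading of the main comparative safety tables and plots. Efficacy and type I error are not affected.

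**Working it through.** **Check against the plan's own figure.** The Synopsis gives 17 pembrolizumab administrations as approximately 1 year. Six weeks to surgery + 6 weeks to the first adjuvant dose + 14 × 3 = 42 weeks gives 54 weeks to the last dose, which agrees. Adjuvant cycle 15 falls in week 1 + 14 × 3 = 43, matching the last column of the schedule in Section 2.2.

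**Inputs for the windows.**
- Arm A surgery, Section 2.1 footnote c: "The timeframe for surgery (after the presurgery visit) is 6 weeks", ±10 days.
- Arm B surgery, Section 9.10.2.1: "Participants in the Treatment Arm B/SoC will proceed directly to surgery following within 4 weeks after randomization".
- Adjuvant start: recommended within 6 weeks of surgery (Section 5.1).
- Radiotherapy after surgery: 6 to 6.5 weeks (Section 9.1.10.1.2).
- Tails: 30/7 = 4.3 weeks for AEs and 90/7 = 12.9 weeks for SAEs.

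**Windows for completers.**
- AE, Arm A: 6 + 6 + 42 + 4.3 = 58.3 weeks.
- AE, Arm B: 4 + 6 + 6.5 + 4.3 = 20.8 weeks.
- AE ratio: 58.3/20.8 = 2.8.
- SAE ratio: 66.9/29.4 = 2.3, if no new anticancer therapy starts within the 90 days.
- Outer limits, Arm A: 4.6 + 0 + 42 + 4.3 = 50.9 to 7.4 + 6 + 42 + 4.3 = 59.7 weeks.
- Outer limits, Arm B: 0 + 6 + 6 + 4.3 = 16.3 to 4 + 6 + 7 + 1 + 4.3 = 22.3 weeks.
- AE ratio limits: 50.9/22.3 = 2.3 to 59.7/16.3 = 3.7. The lower limit starts pembrolizumab on the day of surgery, so it is artificially low.
- Early discontinuation (assumed 21 weeks of adjuvant pembrolizumab): AE ratio 37.3/20.8 = 1.8; SAE ratio 45.9/29.4 = 1.6.

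**Spurious difference with no true effect.** Let pB be the Arm B percentage, r the window ratio and s the share of Arm B's cumulative hazard that falls in the shared surgery/radiotherapy phase. Then

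pA = 1 − (1 − pB)^(s + (1 − s)r).

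For example, pB = 0.10, r = 2.8 and s = 0 give pA = 1 − 0.9^2.8 = 0.255. CIs are unstratified M&N with 714/2 = 357 per arm, assuming all are treated. Entries are percentage points (95% CI).

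| Case | s = 0 | s = 0.5 | s = 0.8 | s = 1 |
|---|---|---|---|---|
| AE 10%, r = 2.8 | 15.5 (10.1 to 21.1) | 8.1 (3.1 to 13.3) | 3.3 (−1.4 to 8.1) | 0 |
| AE 10%, r = 1.8 | 7.3 (2.3 to 12.4) | 3.7 (−1.0 to 8.5) | 1.5 (−3.1 to 6.1) | 0 |
| SAE 5%, r = 2.3 | 6.1 (2.2 to 10.3) | 3.1 (−0.5 to 6.9) | 1.3 (−2.2 to 4.8) | 0 |
| SAE 5%, r = 1.6 | 2.9 (−0.7 to 6.7) | 1.5 (−2.0 to 5.0) | 0.6 (−2.8 to 4.0) | 0 |

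**Effect of adjusting for exposure.** In the first cell the rate is −ln(0.9)/20.8 = 0.51 per 100 person-weeks in both arms, so the rate ratio is 1.0 and the artefact disappears.

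**The case against.** The strongest case against concerns size. The 15.5 points require every Arm A participant to complete 15 adjuvant doses and the hazard to be constant through surgery, radiotherapy and maintenance. After surgery and 60 to 70 Gy, many events that reach the 10% or 5% threshold will be acute reactions in the shared phase, where the artefact is small or nil. At the 1.6 SAE ratio every interval includes zero. The documents give neither the hazard share nor the discontinuation rate. All of this stands as a limit on magnitude; it does not restore comparability for the remaining events.

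Other points carry less weight:
- The CIs are called descriptive. The reason given is multiplicity, which does not correct a displaced point estimate.
- Drug-related summaries set background events aside. They are aggregate rows without CIs and rest on attribution in an open-label trial.
- A year of pembrolizumab is part of the regimen, so the whole-period percentage is a legitimate quantity. That is a reason to keep it, but it does not separate toxicity from observation time.
- The bias runs against the experimental arm, so it tends to overstate harm rather than hide it. It still misinforms the comparison.
- The supplemental SAP might add such a summary. It is not among the documents, and Section 10.6.2 does not defer to it.

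**Conclusion.** The concern holds. The windows follow directly from the protocol's schedule: for completers, about 58 against 21 weeks for AEs and 67 against 29 for SAEs. Section 10.6.2 and Table 15 compare crude percentages across them without adjustment. The mechanism is certain, but the size is not. For an AE seen in 10% of Arm B, the artefact runs from 0 to 15.5 points at the completer ratio and from 0 to 7.3 if adjuvant pembrolizumab averages 21 weeks. These sizes rest on assumed hazard shares, an assumed mean treatment duration and 357 treated participants per arm. The change should be made; the trial's validity does not depend on it.

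**What to change.** Keep the whole-period percentages and CIs in Section 10.6.2 and Table 15, labelled as covering unequal observation periods. State the counting cut-off, including whether late-toxicity records up to Year 5 are counted. Then add:

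1. Between-arm differences with M&N CIs in windows anchored alike in both arms: surgery to 30 days after surgery, and start of radiotherapy to 30 days after its end.
2. Exposure-adjusted incidence rates per person-time of AE observation, by phase: pre-surgery, post-surgery, RT ± cisplatin and pembrolizumab-only, the last shown for Arm A alone.

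The cost is programming and extra tables; the AE, surgery, radiotherapy and dosing dates are already collected. There are two limitations to state. The rates assume a roughly constant hazard within each phase. The anchored windows include only participants who reach surgery or radiotherapy, so those contrasts are not strictly as randomised; neoadjuvant pembrolizumab may also change who is classed as high-risk and receives cisplatin, so the radiotherapy-phase contrast needs that caveat.
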